10.1.5 Causality of adverse events

The causal relationship of each adverse event to the study drug and control drug shall be classified and defined as shown below.

| | |
|-------------|---|
| Related | An adverse event that follows an apparent temporal sequence (including clinical course after discontinuation). Possibly due to the study drug or control drug, although other factors such as underlying disease, concurrent diseases, or concomitant drugs/treatment are also suspected. |
| Not related | An adverse event that does not follow an apparent temporal sequence from administration of the study drug and control drug. Very likely due to other factors such as underlying disease, concurrent diseases, or concomitant drugs/treatment. |

10.1.6 Date of onset

The date of onset of adverse events shall be determined according to the following rules:

| | |
|---------------------|---------------|
| Adverse event, etc. | Date of onset |
|---------------------|---------------|

| | |
|---|---|
| Signs, symptoms, diseases (diagnoses) | The date on which the first signs/symptoms were noted by the research subject and/or the principal investigator or investigator. |
| Asymptomatic diseases | The date on which a diagnosis was confirmed through a test(s). The date on which a diagnosis was confirmed, even when the test results indicate an old sign(s) of the disease or an approximate time of its onset. |
| Exacerbation of concurrent diseases | The date on which the first worsening of diseases/symptoms was noted by the research subject and/or the principal investigator or investigator. |
| Onset of a test abnormality after the start of the study drug administration | The date on which a clinically significant laboratory abnormality was detected. |
| Worsening of a baseline test abnormality after initiation of study treatment | The date on which a clear increase/decrease in a laboratory parameter was clinically confirmed based on the time profile of the parameter. |

10.1.7 Date of resolution

The date of resolution of an adverse event is the date on which the research subject recovered (including resolution with sequelae). If a research subject died due to the adverse event concerned, it shall be the date of death. The adverse event shall be recorded as "ongoing" if the research subject has not yet recovered by the end of the study.

10.1.8 Actions taken for the study drug

Actions taken for the study drug shall be classified or defined as shown below.

| | |
|------------------|---|
| Drug withdrawn | The study drug is discontinued because of an adverse event (including withdrawal by the research subject at his/her own discretion). When the treatment with the study drug is continued after withdrawal from the study, it is defined as "Dose not changed." |
| Dose not changed | The dose was not changed after the onset of the adverse event. The study drug or control drug was discontinued, reduced, or increased because of another adverse event. The study drug was discontinued or reduced for a reason other than the adverse event, e.g., inadvertence of the research subject. |
| Unknown | It has not been possible to determine what action has been taken because the research subject is lost to follow-up. |
| Not Applicable | The administration of the study drug had already been completed or discontinued before the onset of the adverse event. |

| | |
|--------------|--|
| Dose reduced | The dose or control drug was reduced because of the adverse event (including dose reduction by the research subject at his/her own discretion). |
| Washout | The study drug or control drug was suspended (i.e., interrupted) by the research subject at his/her discretion) because of the adverse event (including suspension/interruption, but resumed thereafter. |

10.1.9 Outcome

Outcome of adverse events is classified as follows:

| Category | Criteria |
|-------------------------|--|
| Recovered | Disappearance or recovery of symptoms and findings Laboratory values returned to normal or baseline |
| Improved | The intensity is lowered by one or more stages Symptoms or findings mostly disappeared Laboratory values improved, but have not returned to normal or baseline The research subject died from a cause other than the concerned adverse event while the condition was resolving (recording of the date of death unnecessary) |
| Not recovered | No change in symptoms, findings, or laboratory data The symptoms, findings, or laboratory data on the final day of observable period were aggravated compared with the date of onset Irreversible congenital anomaly The research subject died from another cause before resolution of the concerned adverse event (recording of the date of death unnecessary) |
| Recovered with sequelae | Disability that disturbs daily life |
| Death | Direct relationship between death and the concerned adverse event "Direct relationship" means that the concerned adverse event was the cause of death, or the concerned adverse event was clearly responsible for death. Outcome of an adverse event which was not determined (judged, presumed) a direct cause of death observed in the same research subject is not considered as death. The date of death shall be recorded. |
| Unknown | Follow-up specified in the protocol after the date of onset was not possible due to change of hospitals or relocation, etc. |

10.2 Procedures

10.2.1 Collection and reporting of adverse events

10.2.1.1 Adverse event collection period

Adverse events will be collected for the following periods:

- Any adverse events occurring between the start of study drug administration and completion (or discontinuation) of the treatment period

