7.2 Exclusion Criteria

Patients meeting any of the following criteria will be excluded from this study:

1. Patients with a history of hypersensitivity to ramelteon or melatonin
2. Patients with severe liver disorder
3. Patients who took oral ramelteon within 4 weeks before informed consent
4. Patients who took any oral insomnia medications (including investigational drugs and unapproved drugs) within 2 weeks before the study treatment period
5. Shift workers or night workers
6. Patients with concurrent psychiatric or neurological diseases other than depression which may affect sleep status
7. Patients with a score of ≥ 1 for the HAM-D17 "11: Suicide" item at the start of the run-in period or the start of the study treatment period, or with any suicide attempts within 24 weeks before or during the run-in period
8. Pregnant women, nursing mothers, or women who plan to become pregnant or donate eggs before the informed consent, during the study period or within 4 weeks after the end of the study
9. Patients participating in another investigational or post-marketing clinical trial/study
10. Other patients judged by the principal investigator or investigator to be inappropriate for participation in this study

[Rationale for the exclusion criteria]

1, 2: These criteria are set in consideration of the safety of the participants.

3 to 6: These criteria are set to ensure appropriate evaluation of the efficacy and safety of the study drug.

7, 8: These criteria are set in consideration of the safety of the participants.

9, 10: These criteria are set as essential elements for the study implementation.

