9.1.7 Actigraphy

At the end of the informed consent, an actigraph will be lent to each participant. After full instructions on actigraphy are provided to the participants, actigraphy recording will be started. Patients meeting the inclusion criteria on the basis of the data in the run-in period will keep the actigraph, and be instructed to wear it until the end of the treatment period.

Participants will be instructed to bring the actigraph at each study visit. For analysis of the data recorded in the actigraph, the actigraph will be connected to a computer with an actigraphy data analysis software installed, and the following data will be transferred to the analysis software: sleep latency, total nocturnal sleep time, nocturnal wake time, the number of nocturnal awakenings, sleep efficiency and daytime activity level (step counts). For each of these parameters, the validity of the measured data will be checked according to the "Procedures for actigraphic sleep assessment" prepared separately, and the data during the run-in period (Weeks -1 to 0) and the treatment period (Weeks 3 to 4 and 7 to 8) will be recorded in the case report form. The actigraph device will be retrieved after completion of the actigraphy recording on the 3 occasions, or when the participant is withdrawn from the study.

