9.1.8 Sleep diary

At the end of the informed consent, a sleep diary will be provided to each participant, with instruction on how to keep the diary during the study period. The following diary data during the run-in period (Weeks -1 to 0) and the treatment period (Weeks 3 to 4 and 7 to 8) will be recorded in the case report form: sleep latency, bedtime hour,

awakening hour and number of nocturnal awakenings. Any missing entries, discrepancies, or other potentially dubious entries in the sleep diary will be checked with the participant, and explained in the sleep diary by the participant. Accordingly, necessary additions and corrections will be made to the sleep diary, and recorded in the case report form.

9.1.9 17-item Hamilton Rating Scale for Depression (HAM-D17)

The Hamilton Rating Scale for Depression (HAM-D) is a questionnaire used to rate the severity of depression based on general symptoms of depression, including physical symptoms. The rater will assess individual items on a scale from 0 to 2, 3, or 4 depending on the items, based on an interview with the participant.⁶⁾ The time frame assessed by the HAM-D is one week before each visit. This study will use the 17-item version (HAM-D17), and the scores of individual items and the total score will be assessed and recorded in the case report form.

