10.0 Pretreatment Event and Adverse Event

10.1 Definitions

10.1.1 Adverse events

An adverse event is any untoward medical occurrence in a patient or clinical investigation participant administered a pharmaceutical product (including a study drug) and which does not necessarily have to have a clear causal relationship with this treatment.

An adverse event can therefore be any unfavorable or unintended sign (including an abnormal laboratory finding, for example), symptom, or disease temporally associated with the use of a medicinal product, whether or not considered related to the medicinal product.

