10.1.3 Serious adverse events

Of all the unfavorable medical events that develop with administration of drugs (irrespective of dose), a serious adverse event is an event that:

1. results in death,
2. is life threatening^{*},
3. requires inpatient hospitalization or prolongation of existing hospitalization,
4. results in persistent or significant disability/incapacity,
5. leads to a congenital anomaly/birth defect, or
6. other medically significant condition: a medically important event that causes a risk to a research subject even if it is not immediately life-threatening and does not result in death or hospitalization, or requires an action or treatment to prevent the results described in 1 to 5 above. Points described in the Takeda Medically Significant Adverse Event List (Table 10 (a)) are included in this section.

* The term "life threatening" refers to an event in which the research subject was at risk of death at the time of the event; it does not refer to an event that hypothetically might have caused death if it were more severe.

Table 10.a Takeda Medically Significant AE List

| | |
|--|---|
| Acute respiratory failure/acute respiratory distress syndrome (ARDS) | Hepatic necrosis Acute hepatic failure |
| Torsades de pointes/ ventricular fibrillation/ventricular tachycardia | Anaphylactic shock Acute renal failure |
| Malignant hypertension | Pulmonary hypertension |
| Convulsive seizure (including convulsion and epilepsy) | Pulmonary fibrosis (including interstitial pneumonia) |
| Agranulocytosis | Neuroleptic malignant syndrome/ malignant hyperpyrexia |
| Aplastic anemia | Spontaneous abortion/ stillbirth and fetal death |
| Toxic epidermal necrolysis/ Oculomucocutaneous syndrome (Stevens-Johnson syndrome) | Confirmed or suspected transmission of infection by a medicinal product Confirmed or suspected endotoxin shock |

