10.2.2 Collection and reporting of serious adverse events

When a serious adverse event develops during the period of collecting adverse events, it shall be reported according to the following procedures.

At the time of onset of a serious adverse event or notification of the onset by the research subject, the principal investigator shall report the serious adverse event to the chief executive of the study site immediately, and the sponsor or CRO to whom the sponsor has entrusted responsibility shall notify the principal investigator of the study site.

The principal investigator shall then report the serious adverse event to the sponsor (for the contact information, refer to the attachment) within 1 day of becoming aware of the event onset. Further, the investigator shall submit a formal report within 10 calendar days to the sponsor.

Furthermore, it shall be mandatory to include the contents below in the report to be submitted to the sponsor within 1 working day, and other items shall be reported as far as possible.

- Brief description of adverse event and the reason for why it was determined as serious

- Research subject ID number
- Name of investigator or the subinvestigator
- Name of the study drug
- Determined causal relationship

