10.3.1 Reporting of serious adverse events to Ethics Review Committee and regulatory authorities

When the chief executive of the study site receives a report of a serious adverse event from the investigator, the chief shall consult the Ethics Review Committee, etc., and notify the study sites that are conducting the clinical research through the sponsor or the CRO consigned by the sponsor.

Serious adverse event reported by the principal investigator is unexpected, the chief executive of the study site shall prepare a written report of the unexpected serious adverse event containing the information reported by the principal investigator plus the information below, and submit the report to the Minister of Health, Labor and Welfare, and notify other clinical study sites. (The chief executive of the study site may report it to the Minister of Health, Labor and Welfare via the sponsor, and notify it to other clinical study sites via the sponsor.)

- Actions taken for serious adverse events (discontinuation of new enrollment, revision of informed consent form, re-consents to other research subjects, etc.)
- Date of review, summary of review, result, necessary action, etc., related to Ethics Review Committee, etc.
- Notification to other study sites

The sponsor shall report, in accordance with regulations, unexpected serious adverse drug reactions and other serious adverse events that are subject to emergency reporting to regulatory authorities, the investigators, and directors of study sites.

From the time point of first acknowledging the event or receiving additional information, the sponsor or the CRO consigned by the sponsor shall comply with regulatory required time frames for reporting, and make emergency reports concerning unexpected serious adverse drug reactions and expected serious adverse drug reactions to regulatory authorities. Also, the sponsor shall, in the same way, make an emergency report of other critical safety information that may have a major effect on the study drug risk-benefit, continuation of study drug administration, or continuation of clinical research. The study site shall submit copies of emergency report documents to the Ethics Review Committee, etc.

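### Serious events between signed consent and first dose carry no investigator reporting duty, because the collection window in 10.2.1.1 opens at first dose

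*Protocol*

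**What the plan says.** Three protocol sections form a chain.

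- Section 10.2.1.1 sets the collection period: "Any adverse events occurring between the start of study drug administration and completion (or discontinuation) of the treatment period".
- Section 10.2.2 ties serious-event reporting to it: "When a serious adverse event develops during the period of collecting adverse events, it shall be reported according to the following procedures". The procedures are immediate notice to the chief executive of the site, a report to the sponsor within 1 day, and a formal report within 10 calendar days.
- Section 10.3.1 starts when the chief executive receives the investigator's report. At that point "the chief shall consult the Ethics Review Committee, etc., and notify the study sites that are conducting the clinical research".

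Participation begins before that window opens. Section 9.1.7 states: "At the end of the informed consent, an actigraph will be lent to each participant". The sleep diary starts at the same time (9.1.8), and section 7.3 bars other insomnia drugs from at least 2 weeks before treatment. Exclusion 7 in section 7.2 removes patients with a positive suicide item, "or with any suicide attempts within 24 weeks before or during the run-in period", so the plan itself contemplates a serious event in this interval.

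Section 10.0 is headed "Pretreatment Event and Adverse Event", but no definition, collection period or reporting rule for pretreatment events follows. The file holds two protocol versions, and the sections in this chain read the same in both.

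**The concern.** A consented patient with depression, already wearing the device and kept off other hypnotics, could attempt suicide or be admitted to hospital in the run-in week. The plan foresees the attempt as an eligibility matter but does not ask the investigator to report it as a serious event. At stake is whether the sponsor and the other sites are told promptly, while they could still review screening or the run-in restrictions. This is a patient-safety reporting point, not one about the efficacy estimate.

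**Working it through.** **Tracing the duty to report**

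1. Window: first dose to completion or discontinuation of treatment (10.2.1.1).
2. Investigator's duty: only serious events that develop in that window (10.2.2).
3. Site, ethics committee and other-site steps: start from the investigator's report (first part of 10.3.1).
4. An event after consent and before first dose fails step 2, so step 3 does not start.

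No other section makes the investigator report such an event. Medical history (9.1.2) covers conditions resolved before consent, and concurrent conditions (9.1.14) are those present at consent. The C-SSRS is done at Visits 1 and 2, but its results stay out of the case report form (9.1.12). Adverse events are listed at Visits 3 and 4 (9.3.3, 9.3.4) but not at Visit 2 (9.3.2).

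**How the event would be recorded**

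Section 9.1.16 offers 7 reasons for withdrawal before treatment. None names an adverse event or a sign of suicide; 2 ask for a specified reason (voluntary withdrawal and other). Section 7.5, for withdrawal after dosing, offers 10 reasons, and 2 name these. A run-in suicide attempt would most naturally be coded as an eligibility failure. In the SAP it would appear mainly as a reason in the eligibility table (6.1.2), because section 8 uses the dosed Full Analysis Set.

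**Size of the uncovered interval**

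Inputs: 1-week run-in, 8-week treatment and 30 patients (protocol section 2.0). The documents give no screen-failure rate and no event rate. I assume 0%, 20% or 50% screen failure, and 1 to 10 serious events per 100 patient-years.

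- Share of evaluation time: 7 / (7 + 56) = 11.1%.
- Number consenting: 30; 30 / 0.8 = 37.5, rounded up to 38; 30 / 0.5 = 60.
- Patient-years = number × 7 / 365.25. Expected events = patient-years × rate. P(at least one) = 1 − exp(−expected).

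| Consented | Patient-days | Patient-years | Expected at 1 per 100 (P) | Expected at 10 per 100 (P) |
|---|---|---|---|---|
| 30 | 210 | 0.575 | 0.0058 (0.6%) | 0.058 (5.6%) |
| 38 | 266 | 0.728 | 0.0073 (0.7%) | 0.073 (7.0%) |
| 60 | 420 | 1.150 | 0.0115 (1.1%) | 0.115 (10.9%) |

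The rows for 38 and 60 are upper figures, since some screen failures leave before day 7.

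**The case against.** The strongest defence is that starting collection at first dose is a coherent choice. This is post-marketing research with an approved drug at its approved dosage, and the run-in adds only a wearable device, a diary and a hypnotic restriction. Exclusion 7 keeps a patient who attempts suicide in run-in from being dosed, so the plan does act on the event. That supports leaving non-serious collection where it is. It does not give the sponsor or other sites a report of a serious event in a patient already under study restrictions.

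A reader might infer three stronger things that the documents do not support.

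- *That the definitions also shut out run-in events.* Section 10.1.1 covers any pharmaceutical product, with the study drug as one case, and section 10.1.3 speaks of "unfavorable medical events that develop with administration of drugs (irrespective of dose"), not of study drug. Inclusion 7 requires stable antidepressant medication, so a run-in event can meet both definitions. Only the window excludes it.
- *That nothing in 10.3.1 can apply.* The sponsor's duties later in that section, on emergency reporting and other critical safety information, are not limited to the window. They depend on the sponsor knowing of the event.
- *That the sponsor would not hear in time.* Participants must promptly contact the investigator if they worsen (7.4), symptoms are checked at each visit (10.2.1.2), and an electronic case report form is completed for everyone who consents (12.1), with a reason for withdrawal before treatment (9.1.16). No entry deadline is given, so delay is possible but not shown.

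Safety reports required by a review board (15.1), the guidelines cited in section 1.2, and the investigator responsibilities in Appendix B, which is not in the text available, could also require pre-dose reporting. That limits what can be said about consequences. It does not change what 10.2.1.1 and 10.2.2 say.

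**Conclusion.** The point holds as a gap in the investigator's reporting duty: from signed consent to first dose, the protocol text requires no expedited report of a serious event, and the 10.3.1 steps that depend on that report do not start. Other routes may still bring the event to the sponsor or the review board.

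The size is small. The interval is nominally 7 of 63 days, and about 0.006 to 0.12 events are expected, a 0.6% to 11% chance of at least one. Those figures rest on assumed event and screen-failure rates. The case rests on the low cost of the change and on the plan foreseeing the event, not on its frequency.

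Efficacy results and treatment-emergent tables do not change, because SAP section 5 counts only events with onset after the first dose. This is a cheap improvement, not a defect that threatens the study. The unfilled heading of section 10.0 is clerical and does not strengthen it.

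**What to change.** - In 10.2.1.1 and 10.2.2, collect and report serious events from signed informed consent, whether or not study drug has been taken. Use the existing six seriousness criteria and the procedures of 10.2.2 and 10.3.1. The definitions in 10.1.1 and 10.1.3 can stay.
- Keep non-serious collection from first dose.
- Add one SAP listing of pre-dose serious events for all consented patients, separate from treatment-emergent events. An event that persists into treatment stays pre-dose; a worsening on drug counts as treatment-emergent from the date of worsening.
- Add *adverse event* and *sign of suicide* to the reasons in 9.1.16.

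The cost is a short amendment to three protocol sections, two reason codes, use of the existing adverse event page from consent, one listing and a short site instruction. The downside is a few extra records, mainly in screen failures.
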